### 6.4 Statistical Hypotheses

Not applicable because no formal hypothesis is tested in this study.

### 6.5 Handling of Missing Data and Other Data Issues

This section describes the handling of missing data, and other data issues. Note that the handling of data issues for PK data is described in Section 8.5.4.

[COVID-HIGIV]  
[EBS-CVH-003]

### 6.5.1 Missing Dates

For missing or partial dates for AE, medical history (or prior diagnosis), prior and concomitant medications and procedures, the following conventions will be used for the purpose of determining whether the AE is treatment emergent AE (TEAE), whether the medication/procedure is concomitant or not. Original values will be provided in the listings as is, without imputation.

- For start date missing completely or missing the year, impute the date to the date of first exposure to any study treatment.
- For start date missing both the month and the day, if the year is the same as the date of first exposure to any study treatment, impute the date to the date of first exposure to any study treatment, otherwise, impute the date to January 1st.
- For start date missing the day only, if the year and the month are the same as the date of first exposure to any study treatment, impute the date to the date of first exposure to any study treatment, otherwise, impute the date to the first of the month.
- For end date missing completely or missing the year, impute the date to the date of last contact.
- For end date missing both the month and the day, if the year is the same as the date of last contact, impute the date to the date of last contact, otherwise, impute the date to December 31st.
- For end date missing the day only, if the year and the month are the same as the date of last contact, impute the date to the date of last contact, otherwise, impute the date to the last day of the month.

Note that when the dates are parts of an outcome measure (e.g., the date of death, date of hospital discharge), the imputation rules in this section do not apply. Instead, imputation rules if any, should be described in the next section.

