## 9.2 Adverse Events

AEs will be coded to system organ class (SOC) and preferred term (PT) according to the Medical Dictionary for Regulatory Activities (MedDRA).

AEs reported from the signing of the ICF until immediately before the first dose of IP on Day 1, will be in generally recorded as Medical History, unless it is study procedure associated, which may be considered as non-treatment-emergent AE. A treatment emergent adverse event (TEAE) is defined as an AE that was not present prior to administration of the first dose of study medication and any study procedures and present after the first dose or procedure, or if it represents the exacerbation of an event that was present prior to the first dose or procedure.

Only TEAEs will be included in the summaries described below and 'AE' will refer to TEAE, unless otherwise specified. For AE summaries, an AE occurs on the first dosing date but without onset time will be counted as treatment emergent. AEs with missing start dates, but with stop dates overlapping into the treatment period will also be counted as treatment emergent.

A subject data listing of all AEs (including treatment-emergent AEs (TEAEs) and non-TEAEs) sorted by analysis group, subject ID and AE start date/time will be provided.

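### SAP 6.5.1 has no stop-date check, so it can impute a start after a recorded stop and make an event that ended before dosing treatment-emergent (minor)

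*SAP*

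**What the plan says.** SAP 6.5.1 covers missing or partial dates for adverse events, medical history, medications and procedures. Its conventions are given "for the purpose of determining whether the AE is treatment emergent AE (TEAE), whether the medication/procedure is concomitant or not", so they are classification rules.

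There are three start-date rules:

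- **Nothing known, or year missing:** "For start date missing completely or missing the year, impute the date to the date of first exposure to any study treatment".
- **Month and day missing:** the rule opens "For start date missing both the month and the day, if the year is the same as the date of first exposure". In that case the start becomes the dosing date; otherwise it becomes January 1st of the recorded year.
- **Day missing:** the rule opens "For start date missing the day only, if the year and the month are the same as the date of first exposure". In that case the start becomes the dosing date; otherwise it becomes the first of the recorded month.

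Three further rules complete missing end dates, for the same stated purpose. None of the start-date rules refers to the stop date. The listings keep the dates as recorded.

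SAP 9.2 bears on adverse events only. The definition begins: "A treatment emergent adverse event (TEAE) is defined as an AE that was not present prior to administration of the first dose". It also admits an exacerbation of an event already present. Two counting rules follow: "an AE occurs on the first dosing date but without onset time will be counted as treatment emergent", and "AEs with missing start dates, but with stop dates overlapping into the treatment period will also be counted as treatment emergent". Protocol 9.6.2 likewise requires an event to begin, or to worsen, after study treatment is given.

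SAP 8.2.3 and 9.5.3 describe how prior and concomitant medications are coded and displayed. Neither the SAP nor the protocol separates the two by date.

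**The concern.** A recorded stop date is hard information, and the start-date rules ignore it. When the stop falls before dosing and the start is missing, or is partial in the dosing year or month, the rule produces a start later than the stop. No such record can be true.

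The imputed date then feeds a classification. An adverse event placed on the dosing date without an onset time is treatment-emergent under the SAP 9.2 counting rule, although it was over before the infusion. Adverse events are the primary safety endpoint, and the arms have 8, 8, 8 and 4 subjects, so a single wrong record would be visible in a table. Two programmers, one working from 6.5.1 and the other from the 9.2 definition, could also classify the same event differently.

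**Working it through.** The plan gives no figure on this point to reproduce. The check applies the three start-date rules exactly as written to six hypothetical records. The dosing date of 20 March 2021 is an assumption; the documents give no individual dosing dates.

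**Rule as coded.** Year unknown: dosing date. Only the year known: dosing date if the year is 2021, otherwise 1 January of that year. Year and month known: dosing date if March 2021, otherwise the first of that month.

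| Record | Start recorded | Stop recorded | Start imputed | Start after stop? | On or after dosing by imputed start? | Stop on or after dosing? |
|---|---|---|---|---|---|---|
| 1 | unknown | 15 Mar 2021 | 20 Mar 2021 | yes | yes | no |
| 2 | 2021 only | 10 Feb 2021 | 20 Mar 2021 | yes | yes | no |
| 3 | Mar 2021 | 15 Mar 2021 | 20 Mar 2021 | yes | yes | no |
| 4 | Feb 2021 | 20 Feb 2021 | 1 Feb 2021 | no | no | no |
| 5 | 2020 only | 1 Dec 2020 | 1 Jan 2020 | no | no | no |
| 6 | unknown | 25 Mar 2021 | 20 Mar 2021 | no | yes | yes |

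Three of the five records with a pre-dose stop (1 to 3) receive an impossible start. Records 4 and 5 are handled correctly because the known part of the date does not match dosing. Record 6 is treatment-emergent on either basis.

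**Read as adverse events.** Records 1 to 3 become treatment-emergent by imputed date. Each ended before the infusion, so it was present before the first dose and could not have worsened after it. That fails the definition in protocol 9.6.2, and the SAP 9.2 definition as it relates to the first dose.

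**Read as medications.** Records 1 to 3 become concomitant only if status is taken from the imputed start. If the recorded stop also counts, they are prior.

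**With a stop-date check.** If the dosing date is used only when the stop is on or after dosing, records 1 to 3 become non-treatment-emergent or prior. Records 4 to 6 do not change.

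**Fit with data collection.** Screening is at most 7 days before Day 1, here no earlier than 20 − 7 = 13 March. A stop on 15 March lies inside that window. A stop on 10 February is 18 + 20 = 38 days before dosing and lies well outside it. Record 2 therefore tests the logic of the rule and is not a record the study would be expected to collect.

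**Size of one record.** One subject is 1/8 = 12.5% of an active arm or 1/4 = 25% of placebo.

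**The case against.** Several points on the other side are sound.

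- **SAP 9.2 does not say *only if*.** A reader might infer that 9.2 admits a missing-start event only when its stop date overlaps treatment, and so contradicts 6.5.1 outright. The sentence says such events are also counted, which is an inclusion rule. The conflict comes from the definition of a treatment-emergent event, not from that sentence. The sentence does suggest that the authors meant the stop date to matter.
- **Medications.** A reader might infer that a drug stopped before dosing is necessarily tabulated as concomitant. The documents do not support that. SAP 9.2 is silent on medications, concomitant is not defined, and 6.5.1 supplies end-date rules for the same purpose, which suggests that the end date enters the decision. What stands is that the definition is missing.
- **Few routes into the data.** Protocol 8 starts adverse event capture at the infusion, and protocol 8.5 sends events between consent and dosing to the medical history form. SAP 8.2.2 and 9.2 leave one opening: procedure-associated pre-dose events, which may be held as non-treatment-emergent. The SAP 9.2 definition also mentions study procedures, which blurs the status of exactly these events; protocol 9.6.2 does not. For medications, Screening and Day 1 collect those that are ongoing, so a drug stopped before dosing would mostly have stopped within about a week of it.
- **Visibility.** Listings show the recorded dates, so an error could be traced. SAP 1 also allows derivation details in the table shells, which are not among the documents reviewed here.

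These points limit how often the rule does harm. They do not repair it: 6.5.1, followed literally, still gives a wrong answer, and a listing does not correct a summary table.

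**Conclusion.** The point holds as a minor defect. For a completely missing start date, or a partial one whose known part matches dosing, SAP 6.5.1 can impute a start after a recorded pre-dose stop. For an adverse event, that makes it treatment-emergent against the definitions in SAP 9.2 and protocol 9.6.2. For a medication, the same error arises only if status is read from the imputed start date, which the SAP leaves open.

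The number of affected records cannot be estimated from the documents and is probably small, possibly zero. The 12.5 and 25 percentage points are what any single subject contributes to a table cell; they should not be read as an expected effect. No hypothesis test depends on these tables. The conclusion assumes that the rules are programmed as written and that no correction sits in the table shells.

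**What to change.** Add a condition to the start-date rules in SAP 6.5.1, for example:

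> The start date is imputed to the date of first exposure only if the stop date, after any end-date imputation, is on or after first exposure. Otherwise the start is imputed to the earliest date consistent with its known parts, or to the stop date if the year is unknown, and the record is classed as non-treatment-emergent (AE) or prior (medication or procedure).

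In the check above, this would place the starts of records 1 to 3 at 15 March, 1 January and 1 March 2021, each on or before the recorded stop.

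Also define a concomitant medication in SAP 8.2.3 or 9.5.3 as one taken on or after first exposure, that is, ongoing or with a stop date on or after first exposure. A medication stopped before first exposure is prior.

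The cost is one SAP edit and one programming condition. No new data are needed. Records with a missing stop date that is imputed to last contact after dosing keep the conservative dosing-date rule.

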### 6.5.2 Missing Outcomes and Covariates

Subjects with missing numeric data are treated as missing completely at random (MCAR) when calculating summary statistics.

### 6.5.3 Non-Quantifiable Laboratory Data

For laboratory data, unless otherwise specified in laboratory manuals or assay protocols, values below LLOQ (Lower Limit of Quantification) will be substituted with LLOQ/2; and values above the upper limit of quantification (ULOQ) will be substituted with ULOQ in the calculation of summary statistics; When values reported as “>xx” or “<xx”, xx will be considered as ULOQ or LLOQ, respectively. Original values as collected will be provided in the listings, unless otherwise specified.

[COVID-HIGIV]  
[EBS-CVH-003]

## **6.6 Adjustment for Covariates**

Not applicable because no formal hypothesis is tested in this study.

## **6.7 Multicenter Study**

This study is planned to be conducted at one site - Mount Sinai Hospital at New York of the United States.

## **6.8 Subgroup Analysis**

No subgroup analyses are planned.

## **6.9 Multiplicity Adjustment**

Not applicable because no formal hypothesis is tested in this study.

# **7 STUDY POPULATION CHARACTERISTICS**

## **7.1 Subject Disposition**

Subject disposition over the course of the study will be summarized for all subjects who signed and dated the informed consent form (ICF). Tabulations will include the number of subjects screened, randomized, treated, completed or discontinued study treatment, completed or withdrawn/terminated from protocol-specified follow-up period.

The number and percentage of participants will be summarized by study arms and overall for all randomized subjects. The reasons for study treatment discontinuation or study withdrawal/termination will be summarized by analysis group based on Safety Set.

Disposition data will be listed by subject, incomplete study treatment and/or incomplete study due to COVID-19 pandemic will be indicated. A CONSORT flow diagram will be provided in CSR.

## **7.2 Protocol Deviations**

Important protocol deviations will be summarized by category/sub-category. A listing of all protocol deviations will be provided for all subjects who signed the informed consent form. Protocol deviation due to COVID-19 pandemic will be assessed and indicated in the listing.

# **8 EFFICACY ANALYSIS**

## **8.1 Data Sets Analyzed**

A summary of subjects included in each analysis set will be provided. Detailed listings will be provided for each subject that was excluded from each analysis set, including the reasons for exclusion.

[COVID-HIGIV]  
[EBS-CVH-003]

## 8.2 Demographics and Baseline Characteristics

### 8.2.1 Demographics

The following demographics and baseline characteristics will be summarized as continuous variables using descriptive statistics (n, mean, SD, median, minimum, and maximum) by treatment group for all subjects in the Safety set:

- Age (years)
- Baseline weight (kg)
- Baseline height (cm)
- Baseline BMI

The following demographics and baseline characteristics will be summarized as categorical variables with counts and percentages by treatment group and overall for Safety set:

- Sex (Female, Male)
- Race (American Indian or Alaska Native, Asian, Black or African American, Native Hawaiian or Other Pacific Islander, White, Multiracial, and Other)
- Ethnicity (Hispanic or Latino, Not Hispanic or Latino, Unknown)

Subject demographics and baseline characteristics data listing will be provided.

### 8.2.2 Medical History

Medical history will be coded to system organ class (SOC) and preferred terms (PT) using the Medical Dictionary for Regulatory Activities (MedDRA) dictionary. AEs reported from the signing of the ICF until immediately before the first dose of IP on Day 1, will be generally recorded as Medical History, unless it is study procedure associated, which may be considered as non-treatment-emergent AE. A listing of medical history will be provided.

### 8.2.3 Prior Medications

Prior medication, concomitant medications will be coded using WHO-Drug. The number and percentages of subjects taking each drug, by ATC level 4 and preferred terms will be summarized by treatment group.

## 8.3 Treatment Compliance

Subjects with incomplete study treatment (i.e., partial infusion) or infusion interruption will be summarized by reason for incompletion and by analysis group for Safety set.

Study drug administration data, such as infusion volume (saline for placebo arm, COVID-HIGIV for other arms), and overall infusion duration will be summarized by analysis group as well.

[COVID-HIGIV]  
[EBS-CVH-003]

A subject listing of study drug administration will be provided including infusion start/end date and time, pharmacist prepared, and subject received infusion volume, infusion duration, and if any infusion interruption the reason(s).

#### **8.4 Efficacy Analysis**

There are no efficacy endpoints and efficacy analyses in this study.

#### **8.5 Pharmacokinetic Evaluation**

##### **8.5.1 Serum Concentration Data**

Serum concentration of SARS-CoV-2 antibody is measured by two assays:

- Binding IgG Immunoassay
- Pseudovirus Neutralization Assay

The assays have been validated for PK assessments, with a lower limit of quantitation (LLOQ) value of \_\_\_\_\_ and the upper limit of quantitation (ULOQ) value of \_\_\_\_\_ for the binding immunoassay; and LLOQ of \_\_\_\_\_ and ULOQ of \_\_\_\_\_ for pseudovirus neutralization assay.

Subjects with incomplete data will be evaluated on a case-by-case basis to determine if sufficient data are available for reliable estimation of PK parameters.

A listing of PK sample collection times will be provided, with flags to indicate sampling time deviations.

##### **8.5.2 Pre-Dose Concentration Values and Endogenous Compounds**

The anti-SARS-CoV-2 IgG is not expected in study participants because a negative rapid anti-SARS-CoV-2 IgG/IgM antibody test result is required for inclusion. A pre-dose serum sample for SARS-CoV-2 antibody was drawn on Day 1. Any anomalous concentration values observed prior to the first dose will be identified and may be excluded from PK analysis or statistical summaries. If necessary (e.g., anomalous pre-dose concentration detected in multiple subjects), background subtraction will be applied before the concentration values are used in PK analysis or statistical summaries.

##### **8.5.3 Exclusion of Outliers**

Individual serum concentrations may be excluded from the analysis because they are erroneous or abnormal at the discretion of the study team following a review of available documentation (e.g., bioanalytical report, validation report). Any such exclusion will be clearly listed in the study report along with justification for exclusion.

Entire serum concentration-time profiles for a participant may be excluded following review of available documentation (e.g., bioanalytical report, validation report, and protocol

[COVID-HIGIV]  
[EBS-CVH-003]

deviation log) as determined by the study team. Any such exclusion will be clearly listed in the study report along with justification for exclusion.

Any excluded data will be flagged in the individual data listings.

#### 8.5.4 Non-Quantifiable and Missing Concentrations

If a concentration value is below the LLOQ,

- Individual concentration listings in the CSR should list these concentrations as “<LLOQ”.
- For the calculation of concentration summaries and plotting mean and individual concentration-time profiles, concentration values <LLOQ are imputed with LLOQ/2.

For the purpose of calculating PK parameters,

- Missing pre-dose values, pre-dose concentrations and concentrations prior to the first quantifiable concentration that are <LLOQ are set to 0 (zero) and included in the analysis.
- A value of <LLOQ after  $C_{max}$  that is between two quantifiable data points or after the last quantifiable concentration value at the end of the collection interval will be treated as missing and excluded from the analysis.

If a concentration value is “>ULOQ”, the ULOQ threshold will be imputed for PK parameter estimate and descriptive statistics calculation. Individual concentration listings in CSR will report the concentration as “>ULOQ”.

Missing concentration values are left as missing and excluded from the analysis.

#### 8.5.5 PK Parameters

PK parameters in [Table 2](#) will be derived from the concentration-time data by non-compartmental methods using actual sampling times. If the actual sampling time is missing, but a valid concentration value has been measured, the nominal time as specified in the protocol may be used.

Non-compartmental PK parameter calculations and graphics will be implemented using SAS version 9.4 or higher.

**Table 2: PK Parameters for COVID-HIGIV**

Parameter	Definition and Calculation
$C_{max}$	Maximum observed serum concentration after a single dose (. If there are missing data near the expected $C_{max}$ , it may be set to missing after team review.
$C_{max}BWN$	Body weight normalized $C_{max}$

[COVID-HIGIV]  
[EBS-CVH-003]

$T_{max}$	Time of maximum observed serum concentration, if $C_{max}$ exists.
$C_{min28d}$	Minimum observed or estimated serum concentration on the day of 28 days post-dose after a single dose.
$C_{min28d}BWN$	Body weight normalized $C_{min28d}$
$\lambda_z$	Apparent first order terminal elimination rate constant. It is calculated by linear regression analysis of log concentration values that include consecutive data points in the terminal phase (i.e., including the last quantifiable value, preferably not include $C_{max}$ ) that maximizes the adjusted $r^2$ . A minimal of 3 data points is required for determination. If the maximum adjusted $r^2$ is $< 0.700$ , it is considered as not estimable and the $\lambda_z$ will be listed but not included in statistical analyses.
$T_{1/2}$	Terminal elimination half-life, or just referred to as half-life. It is calculated as $((\ln 2)/\lambda_z)$ , when $\lambda_z$ can be estimated.
$AUC_{0-14d}$	Area under the serum concentration-time curve (AUC) from time 0 to 14 days. Time 0 is defined as the end time of IP administration of a single dose. AUC is calculated using linear-up log-down trapezoidal summation. A minimal of 3 non-LLOQ concentration values is required.
$AUC_{0-14d}BWN$	Body weight normalized $AUC_{0-14d}$
$AUC_{0-28d}$	AUC from time 0 to 28 days.
$AUC_{0-28d}BWN$	Body weight normalized $AUC_{0-28d}$
$AUC_{0-last}$	AUC from time 0 to the last quantifiable concentration after a single dose. A minimal of 3 non-LLOQ concentration values is required.
$AUC_{0-last}BWN$	Body weight normalized $AUC_{0-last}$
$AUC_{0-inf}$	AUC extrapolated to infinity after a single dose. It is calculated as $AUC_{0-last}$ plus the additional area extrapolated to infinity using the linear regression line for the calculate of $\lambda_z$ . If $\lambda_z$ cannot be estimated $AUC_{0-\infty}$ will not be calculated. If the percentage of extrapolated area exceeds 40% of the estimated $AUC_{0-\infty}$ , the $AUC_{0-\infty}$ value will be listed but not included in statistical analyses.
$AUC_{0-inf}BWN$	Body weight normalized $AUC_{0-inf}$
CL	Apparent systemic clearance. It is calculated as $(\text{Dose} / AUC_{0-inf})$ . Note that the dose needs be measured by the same PK assay and expressed in the same unit.
$V_z$	Apparent volume of distribution (during the terminal phase). It is calculated as $(CL / \lambda_z)$ .

[COVID-HIGIV]  
[EBS-CVH-003]

### 8.5.6 Pharmacokinetic Analysis

All PK summary analyses will be conducted based on the PKS. Listings of PK concentration will be presented based on the COVID-HIGIV treated subjects with a flag indicating data points excluded from the PK analyses. Listings of PK parameters will be based on COVID-HIGIV treated subjects, with an indicator for parameter(s) considered as unreliable and being excluded from the summary analysis. A listing for the excluded subjects will be provided with reasons for exclusion.

PK concentration data will be summarized by nominal time points. The summary statistics for concentration data include n, arithmetic mean (Mean), standard deviation (SD), median, minimum (Min), maximum (Max), geometric means (Geo. Mean), and geometric percentage coefficient of variation (Geo. CV%).

PK parameters in [Table 2](#) will also be summarized with the descriptive statistics list above. Summary of  $T_{max}$  will include n, median, minimum, and maximum only. The Geo. CV% is calculated as,

$$\text{Geo. CV\%}(x) = 100 * (\sqrt{\exp(\text{variance of log}(x))} - 1), x = \text{PK concentrations}$$

Scatterplots for individual PK concentration-time profiles will be presented.

To investigate the dose proportionality of body weight normalized  $AUC_{0-14d}$  and  $C_{max}$  (if data permit), the power model will be used which fits a linear regression model with the log PK parameter against the log dose (COVID-HIGIV dose in mg/kg unit), i.e.,

$$\log(\text{PK parameter}) = \text{intercept} + \text{slope} * \log(\text{COVID-HIGIV dose})$$

Estimates of the intercepts and slopes along with 90% CIs will be reported. If the assumption of linearity is considered acceptable (i.e., adjusted  $r^2 > 0.8$ ) and if the 90% CI for the slope is entirely with (0.9, 1.1), the relationship between dose and the PK parameter will be concluded to be dose proportional for the dose range studied.

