## **9.6 Planned Method of Analyses**

In general, continuous endpoints will be summarized by descriptive statistics including number of subjects, mean, standard deviation (SD), median, minimum and maximum. Logarithmic transformation will be used when appropriate, coefficient of variation (CV), geometric mean, and geometric CV will also be summarized. Categorical endpoints will be summarized by the total number of subjects, frequencies and percentages. Unless otherwise specified, CIs are two-sided with 95% confidence. Non-compartment method will be used for estimating PK parameters.

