## 6 STATISTICAL CONSIDERATIONS

### 6.1 General Considerations

Data summaries will be tabulated by appropriate grouping for each analysis population as specified in [Section 5.3](#).

Continuous endpoints will be summarized by descriptive statistics including number of non-missing observations (n), mean, standard deviation (SD), median, minimum, and maximum. When log-normal distribution is appropriate, logarithm transformation will be used and geometric mean (Geo. Mean) and geometric coefficient of variation as a percentage (Geo. CV%) will be reported. Categorical variables will be summarized by counts (n) and percentages of subjects (%) in each category, including missing or unknown when appropriate.

Unless otherwise specified, confidence intervals (CIs) are two-sided at 95% confidence level.

All derivations, statistical analyses, summaries, and listings will be generated using SAS Version 9.4 or higher (SAS Institute, Inc., Cary, North Carolina, United States).

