### 6.2 Units and Precision

All clinical laboratory data and vital sign data will be reported using US convention units. Measures with non-standard units include:

- Anti-SARS-CoV-2 IgG Binding Titer: AU/mL, binding antibody titers normalized to reference standard ([Appendix VI](#)).

[COVID-HIGIV]  
[EBS-CVH-003]

- Anti-SARS-CoV-2 Pseudo-virus Neutralizing Antibody Titer: AU/mL, neutralizing antibody titers normalized to reference standard ([Appendix VI](#)).
- All PK concentrations will be reported in listings and analyzed with the same precision (with 1 decimal place) as the source data provided by the bio-analytical laboratory, unless otherwise specified. For derived PK parameters, the following convention will be used:
  - Elapsed time from dosing will be expressed as hours or days in the calculations and rounded to two decimal places.
  - Parameters derived directly from source data (e.g., Cmax, Tmax, minimum, maximum) or first-order statistics (e.g., mean) will be reported and analyzed with the same precision as the source data.
  - Second-order statistics (e.g., SD) will be reported with one more significant digit than the source data.
  - Percentages (including Geo. CV%) will be reported to one decimal place.
  - Ratios of means for PK parameters will be presented with two decimal places.

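### SAP 8.5.6 prints the geometric CV formula with the −1 outside the square root, so Geo. CV% in the PK tables would be understated if coded as printed

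*SAP*

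**What the plan says.** SAP section 8.5.6 defines Geo. CV%(x) as "100 * (\sqrt{\exp(\text{variance of log}(x))} - 1" with the outer bracket then closed. As printed, the root covers only the exponential of the log-variance, and the 1 is taken off afterwards. The line defines x as PK concentrations only. Just before it, however, the same section says that the PK parameters of Table 2 "will also be summarized with the descriptive statistics list above", a list that includes Geo. CV%. Tmax is the exception and gets only n, median, minimum and maximum.

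The other places name the statistic without defining it:

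- SAP section 6.1, for data treated as log-normal, says that "logarithm transformation will be used and geometric mean (Geo. Mean) and geometric coefficient of variation as a percentage (Geo. CV%) will be reported".
- SAP section 6.2 sets the precision: "Percentages (including Geo. CV%) will be reported to one decimal place".
- Protocol section 9.6 says "coefficient of variation (CV), geometric mean, and geometric CV will also be summarized".

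Nothing in either document supplies a second formula that would override the one in 8.5.6. The SAP revision to version 1.1 changed the binding-assay ULOQ and a reference, not this line.

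**The concern.** Section 6.1 ties the statistic to a log-normal model, and under that model the geometric CV has the −1 under the root. The printed expression is a different quantity. It is not the other statistic sometimes given the same name either, 100 × (exp(SD of ln x) − 1).

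PK is one of the two primary objectives, no hypothesis is tested, and the sample size is justified only as adequate for description. The descriptive PK tables are therefore a main product of the trial, and Protocol section 1.3 says the PK parameters will feed dose selection. Geo. CV% is the measure of spread that accompanies the geometric mean in those tables, for both assays, for concentrations at each nominal time and for every Table 2 parameter except Tmax. Coded as printed, it would make between-subject variability look much smaller than it is, while the mean and SD in the same tables showed otherwise.

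**Working it through.** **Inputs.** The printed formula is from SAP 8.5.6, the log-normal basis from SAP 6.1 and the one-decimal precision from SAP 6.2. The documents state no Geo. CV% and no log-scale variance, so there is no figure of the plan's to reproduce. The true CVs below are assumptions chosen to span a wide range.

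**Formulas.** Let v be the variance of ln(x).

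- (a) As printed: `100 × (sqrt(exp(v)) − 1)`
- (b) Log-normal geometric CV: `100 × sqrt(exp(v) − 1)`
- (c) The other variant in use: `100 × (exp(sqrt(v)) − 1)`

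**Direction.** Put y = exp(v/2), so y > 1 whenever v > 0. Then (a)/100 = y − 1 and (b)/100 = sqrt(y² − 1) = sqrt((y − 1)(y + 1)). Because y + 1 > y − 1, (b) exceeds (a) for every v > 0. A numerical grid of v from 0.001 to 20 found no exception. At v = 0, for example when all values at a time point are imputed as LLOQ/2, both forms give 0%.

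**Size.** If the true CV, as a fraction, is c, then v = ln(1 + c²) and exp(v) = 1 + c². The printed form reduces to `100 × (sqrt(1 + c²) − 1)`. For c = 0.30 this is 100 × (sqrt(1.09) − 1) = 4.4%.

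| True geometric CV (assumed) | Reported by the printed form | Understated by a factor of |
|---|---|---|
| 10% | 0.5% | 20.1 |
| 20% | 2.0% | 10.1 |
| 30% | 4.4% | 6.8 |
| 50% | 11.8% | 4.2 |
| 100% | 41.4% | 2.4 |
| 133.3% | 66.7% | 2.0 |
| 200% | 123.6% | 1.6 |

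**Is it variant (c)?** At c = 0.30, v = ln(1.09) = 0.0862 and sqrt(v) = 0.2936. Form (b) gives 30.0%, form (c) gives 34.1% and the printed form gives 4.4%. It matches neither.

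**Base of the logarithm.** The line says log without naming the base. Pairing it with exp() implies natural log. If base 10 were used by mistake, a natural-log SD of 0.3 would give 13.1% from form (b) instead of 30.7%, so the base is worth stating.

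**The case against.** The algebra is not in dispute. The strongest reply is that the point rests on where a root sign ends in an equation extracted from a PDF, which is easily misread. The correct formula typed on one line, with the root sign before a bracket holding exp(...) − 1, has the same set of brackets as the extracted text, and the two differ only in which side of the opening bracket the root sign sits. The outer bracket is therefore weak support for the printed reading and not proof. This stands, and it is why the source page must be checked first.

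It also stands that SAP section 1 leaves some detail on derived variables to programmer's notes in the TLF shells. Neither these nor the SAS code are in the documents, so whether the printed form was ever coded is unknown.

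The consequence is limited as well. Geo. CV% is descriptive, no decision rule uses it, and the dose-proportionality conclusion depends only on the slope's 90% CI and the adjusted r². A Geo. CV% near 4% beside an SD near 30% of the mean might be noticed. But that safeguard relies on a reader spotting an inconsistency that the SAP itself would have created, and it does not make the formula right. The incomplete definition of x is mainly editorial.

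**Conclusion.** The concern holds. As printed, the SAP's only definition of Geo. CV% is wrong for a log-normal geometric CV and understates it for every non-zero variance: by a factor of about 20 at a true 10%, 6.8 at 30%, 4.2 at 50% and 2.4 at 100%. These factors rest on assumed CVs, and no single one should be taken as the effect in this trial.

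The conclusion about the tables is conditional on the root sign being in the source as it appears in the extracted text and on the formula being programmed that way. Only Geo. CV% is affected. Geometric means, the other PK point estimates and the power-model slope with its interval are unchanged. It should be fixed because it is a stated computing rule for the summary tables of a primary objective, but it does not threaten the trial's other conclusions.

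**What to change.** Check the extent of the root sign in the source PDF. If it is as printed, replace the line in SAP 8.5.6 with `Geo. CV%(x) = 100 × sqrt(exp(variance of ln(x)) − 1)`, writing ln so that the base is explicit, and define x as PK concentrations and PK parameters. Confirm that the programmer's notes in the TLF shells and the SAS code use the same expression. If the root sign turns out to be correct in the source, the clarification of x and of the log base is still worth making.

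The cost is one line of SAP text and, if the printed form was coded, one line of code and a rerun of the affected PK tables. No other result changes.
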